## **5. AMENDMENTS AND UPDATES**

None

## **6. MILESTONES**

Milestone	Planned Date
Feasibility assessment	Jun 2019
Protocol finalization	Dec 2019
Statistical and epidemiological analysis plan	Mar 2020
Start of data collection	DD Month YYYY
End of data collection	DD Month YYYY
Statistical and epidemiological analysis report	Mar 2020
Final results	Apr 2020
Clinical study report	Apr 2020
Final report of study results:	Apr 2020

## 7. RATIONALE AND BACKGROUND

Stroke is the leading cause of mortality in China, resulting in about 1.9 million deaths in 2013 [P20-03289]. Intravenous recombinant plasminogen activator (IV-rtPA) has been demonstrated to be essential to decrease disability among acute ischemic stroke (AIS) patients. However, currently a large number of stroke patients who have arrived hospitals on time and with no documented absolute contraindications for IV-rtPA are not receiving the thrombolysis treatment in China [P14-16838]. Since 2015, Chinese government and professional societies have put a lot of efforts in improving the quality of stroke care, including supporting hospitals to build stroke centers/units, encouraging stroke centers to submit thrombolysis treatment data, and issuing stroke care quality reports.

The China National Stroke Registry (CNSR), sponsored by the China Ministry of Health (MOH), is a nationwide hospital-based, prospective stroke registry for patients presented to hospitals with acute cerebrovascular events. The primary objectives of CNSR are to evaluate the quality of care during the acute hospitalization phase for cerebrovascular patients. The objectives are evaluated based on the performance indicators for stroke care delivery, and factors associated with the performance indicators are identified. The secondary objectives of CNSR include measuring longitudinal trends in clinical/functional outcomes of cerebrovascular patients at 3 months, 6 months, and 12 months after disease onset, the relationship between the clinical/functional outcomes of the patients with the quality of care during acute hospitalization, and adherence of the patients to secondary stroke prevention medication [P11-07866]. Patients had been continually enrolled for 8-12 months every five years since 2007. Data collected for each patient included demographics, medical history, initial, National Institutes of Health Stroke Scale (NIHSS) score, time intervals related to symptom onset, hospital arrival, and IV-rtPA treatment during the acute hospitalization phase.

Till 2017, three waves of CNSR were completed: 2007-2008 (CNSR I), 2012-2013 (CNSR II), and 2015-2017 (CNSR III). The number of hospitals participating each of CNSR were 132, 219, and 201, respectively. When compared to CNSR I, data from CNSR II showed a 1.17-fold increase in the adjusted odds of delivering evidence-based performance metrics for ischemic stroke (IS) care. Nevertheless, no statistically significant difference in the proportion of patient who received intravenous thrombolytics (IVT) treatment within 3 hours (h) of symptom onset was observed between the two CNSR [P20-03289].

In China, IV-rtPA was approved for the treatment of AIS patients within 3h of symptom onset without absolute contraindications. However, in 2008, the European Cooperative Acute Stroke Study (ECASS) III study concluded that AIS patients could still benefit from IV-rtPA treatment when given between 3h and 4.5h [P08-12177]. The Chinese treatment guideline for AIS was updated in 2010, for which a recommendation of IV-rtPA treatment within 3h to 4.5h of symptom onset was added [P20-03291].

The current study aims at evaluating differences, if any, in clinical practice of IV-rtPA treatment among AIS patients from 2007 to 2017. In addition, the study will also provide information on the demographic and clinical characteristics of AIS patients receiving IV-rtPA in China. Taken together, the study will help us to better understand the trend of clinical practices for AIS treatment in China during the last decade, especially after the update of the

national AIS treatment guideline and the continuous efforts made by academic society and MOH in the field of stroke care.

## **8. RESEARCH QUESTION AND OBJECTIVES**

The present study is to be conducted based on the AIS patient data collected from CNSR I, II, and III.

The primary objectives are:

- To investigate the temporal changes in the proportion of IV-rtPA treatment from 2007 to 2017 among IVT-eligible patients (patient groups B and B') and overall AIS patients (patient group A) in China;
- To investigate the temporal changes in IV-rtPA treatment time intervals from 2007 to 2017 among IV-rtPA-treated patients (patient groups C and C') in China.

The secondary objectives are:

- To describe the demographic and clinical characteristics of the IV-rtPA-treated patients (patient groups C and C'), IVT-eligible patients (patient groups B and B') and the overall AIS patients (patient group A) from 2007 to 2017 from the CNSR I to III.

## 9. RESEARCH METHODS

### 9.1 STUDY DESIGN

This is a non-interventional study based on existing data. We will analyze data from three cross-sectional surveys of AIS patients in China: CNSR I (2007-2008), II (2012-2013), and III (2015-2017).

[figure not shown]
### 9.2 SETTING

In this study, AIS patient data from CNSR I to III will be used. The study will analyze data for the following patient groups:

- (1) All AIS patients (patient group A): the overall AIS patients aged 18-80 years who arrived at hospital within 7 days of symptom onset;
- (2) IVT-eligible patients (patient groups B and B'): AIS patients who arrived at hospital within 2h (patient group B) and 3.5h (patient group B') of symptom onset and with no documented absolute contraindications to IVT treatment;
- (3) IV-rtPA-treated patients (patient groups C and C'): IVT-eligible patients who arrived at hospital within 2h of symptom onset and received IV-rtPA within 3h of symptom onset (patient group C) and those who arrived at hospital within 3.5h of symptom onset and received IV-rtPA within 4.5h of symptom onset (patient group C').

The flow of data selection for each of the three reporting patient groups is depicted in [Figure 1](#) below.

Figure 1 Patient groups selected for the time-trend study

The in- and exclusion criteria for each of the reporting groups are listed below:

**1) All AIS patients (patient group A)**

1. Inclusion criteria:

- (1) Aged 18-80 years
- (2) Diagnosed with AIS on admission

2. Exclusion criteria:

- (1) Missing baseline data including age and gender
- (2) Diagnosed with intracranial hemorrhage (ICH), Transient Ischemic Attack (TIA), subarachnoid hemorrhage (SAH), or unspecific stroke
- (3) Arrived at hospital after 7 days of symptom onset

**2) IVT-eligible patients (patient groups B and B')**

1. Inclusion criteria:

- (1) Met the in- and exclusion criteria of "all AIS patients"
- (2) Arrived at hospital within 2h (patient group B) or 3.5h (patient group B') of symptom onset

2. Exclusion criteria:

- (1) Missing key data including
  - i. symptom onset time (or last known well time);
  - ii. hospital arrival time;
  - iii. whether received IVT treatment or not;
  - iv. the time of IVT treatment
- (2) Documented IVT absolute contraindications, according to the case report form (CRF) for each wave of CNSR (please refer to [ANNEX 3](#) for details)

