**3) IV-rtPA-treated patients (patient groups C and C')**

1. Inclusion criteria:

- (1) Met the in- and exclusion criteria of "IVT-eligible patients"
- (2) Treated with IV-rtPA within 3h (patient group C) or 4.5h (patient group C') of symptom onset

2. Exclusion criteria:

- (1) Not received IVT
- (2) Received IVT other than rtPA
- (3) Treated with IV-rtPA after 3h (patient group C) or 4.5h (patient group C') of symptom onset
- (4) Received additional treatments with intra-arterial reperfusion or experimental therapies

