2. Diagnosed with intracranial hemorrhage (ICH), Transient Ischemic Attack (TIA), subarachnoid hemorrhage (SAH), or unspecific stroke
3. Arrived at hospital after 7 days of symptom onset

IVT-eligible patients (patient groups B and B')**Inclusion criteria:**

1. Met the in- and exclusion criteria of "all AIS patients" (Group A)
2. Arrived at hospital within 2h (patient group B) or 3.5h (patient group B') of symptom onset

Exclusion criteria:

1. Missing key data including
 - I. symptom onset time (or last known well time);
 - II. hospital arrival time;
 - III. whether received IVT treatment or not;
 - IV. the time of IVT treatment
2. Documented IVT absolute contraindications, according to the case report form (CRF) for each of CNSR

IVT Absolute Contraindications according to CRFs for each of CNSR:**For CNSR I:**

- Aged above 80 years;
- CT evidence of intracranial haemorrhage;
- CT evidence of early signs of large cerebral infarction;
- Concurrence of epileptic seizures during ischemic stroke;
- Have suffered a stroke or severe head injury in the past 3 months;
- Uncontrolled hypertension despite active treatment. Uncontrolled hypertension refers to systolic blood pressure > 185 mmHg or diastolic blood pressure > 110 mmHg, measured at least 10 minutes apart and repeated 3 times;
- Known haemorrhagic condition with significant bleeding disorder at onset or within the past 6 months;
- Acute pancreatitis or proven ulcerative gastrointestinal disease within 3 months;
- Recent invasive cardiopulmonary resuscitation or childbirth within 10 days. Non stress vascular puncture (such as subclavian vein or femoral vein puncture);
- Blood glucose < 50 mg/dl (2.7 mmol/l) or > 400 mg/dl (22.2 mmol/l);
- Platelet count < 105/mm³;
- Prothrombin time (PT) (international normalized ratio [INR]) > 1.5 or PT > 15 or activated partial thromboplastin time (APTT) > 40 sec.

For CNSR II and III:

- Uncontrolled hypertension despite active treatment. Uncontrolled hypertension refers to systolic blood pressure > 185 mmHg or diastolic blood pressure > 110 mmHg;
- Concurrence of epileptic seizures during ischemic stroke;
- Recent surgery or trauma within 15 days;

- Recent intracranial or spinal surgery, head trauma, or stroke within 3 months;
- Previous history of intracranial haemorrhage, aneurysm, vascular malformation, or brain tumour;
- Active visceral bleeding within 22 days;

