10.3 HANDLING OF INCONSISTENCIES IN DATA AND QUTLIERs

Missing and erroneous values in patient cases can significantly impact the ability to perform research for identifying risk factors and disease distribution, treatment progression. This study is mainly based on review of data collected from CNSR I, II, III and aims at evaluating differences in clinical practice of IV-rtPA treatment among AIS patients from 2007 to 2017. Data follow-up period has already been finished. Thus, data cannot meet the criteria of this study will be excluded.

Exclusion criteria:

1. Missing key data including
 - symptom onset time (or last known well time);
 - hospital arrival time;
 - whether received IVT treatment or not;
 - the time of IVT treatment
 - age and gender
2. Contradiction of time period:
 - IVT treatment time earlier than symptom onset time (or last known well time);
 - treatment time earlier than hospital arrival time;
 - hospital arrival time earlier than symptom onset time
3. Diagnosed with intracranial hemorrhage (ICH), Transient Ischemic Attack (TIA), subarachnoid hemorrhage (SAH), or unspecific stroke
4. Arrived at hospital after 7 days of symptom onset

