11.1 MAIN ANALYSIS

Patient group A includes patients aged 18-80 years and diagnosed with AIS on admission. Patients with missing baseline data including age and gender and diagnosed with intracranial hemorrhage (ICH), Transient Ischemic Attack (TIA), subarachnoid hemorrhage (SAH), or unspecific stroke and arrived at hospital after 7 days of symptom onset will be excluded.

Patient group B and patient group B' are both based on patient group A. And patients with missing key data will be excluded from patient group B and patient group B', including symptom onset time or last known well time, hospital arrival time, whether received IVT treatment or not and the time of IVT treatment.

Patients documented with IVT absolute contraindications, according to the case report form (CRF) for each of CNSR will be also excluded from patient group B and patient group B'.

Patients group B included patients who arrived at hospital within 2h of symptom onset.

[figure not shown]
Patients group B' included patients who arrived at hospital within 3.5h of symptom onset.

Patient group C is based on patients group B and patient group C' is based patient group B'. And both patient group C and patients group C' are to meet the inclusion criteria of "IVT-eligible patients". Patients not received IVT or received IVT other than rtPA or received additional treatments with intra-arterial reperfusion or experimental therapies will be excluded. Patients group C included patients who were treated with IV-rtPA within 3h. Patients group C' included patients who were treated with IV-rtPA within 4.5h.

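### The missing-IVT-time exclusion for B and B' can act only on treated patients, so both primary denominators are selected on treatment; the wording needs a limit and Table 1 needs bounds

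*Protocol*

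**What the plan says.** Protocol 9.2 defines IVT eligibility by arrival within 2h (B) or 3.5h (B') of onset and by the absence of a documented absolute contraindication. It then excludes patients with missing key data, of which the fourth item is "iv. the time of IVT treatment". The Protocol abstract carries the same list. SAP 7.2 repeats it ("IV. the time of IVT treatment"), and SAP 11.1 names, among the data whose absence excludes a patient from B and B', "whether received IVT treatment or not and the time of IVT treatment". None of these places says that the item applies only where IVT was given.

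SAP 10.3 adds contradiction rules, including "treatment time earlier than hospital arrival time" and IVT earlier than onset, under the general statement "Thus, data cannot meet the criteria of this study will be excluded". It does not say which group these rules act on.

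The treated groups C and C' must first satisfy the B/B' criteria. Only at that later step does Protocol 9.2 remove patients under "Not received IVT" and "Received IVT other than rtPA", along with late rtPA and added intra-arterial or experimental therapy. Group A is "the overall AIS patients aged 18-80 years who arrived at hospital within 7 days of symptom onset" and has no exclusion for a missing IVT time. The primary outcomes are C/B and C'/B' (Table 1); the secondary proportions are C/A and C'/A (Table 3.1).

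**The concern.** Whether a patient was eligible should not depend on whether the patient was treated. A patient not given IVT has no IVT time that could be missing or contradictory, and unknown IVT status is already excluded by the third item. In practice, then, the fourth item and the treatment-time contradiction rules can remove only patients recorded as given IVT, and each removal leaves the denominator as well as any place in the numerator.

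Two things follow. First, both primary proportions can be shifted. The trend across waves can be shifted too if unusable times are more common in one wave than another. Data capture moved from paper forms (wave I) to a web CRF (II) to an electronic system (III), so this is possible. Second, the tables treat the same patient differently. Under Protocol 9.2, an rtPA-treated patient with no recorded time stays in group A and counts as not treated in-window in Table 3.1, but disappears from Table 1.

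**Working it through.** **Inputs from the documents.** Assumed proportions p = 4%, 5%, 28% and total AIS patients 14704, 19604, 15204 (Protocol 9.5); wave I total 12415 in SAP 7.2.

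**Inputs that are assumptions.** x = share of B dropped; q = share of the dropped patients who truly belong in C; m = share of true numerator cases without a usable IVT time (5% to 30% tried). The documents give none of these.

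**Step 1: the plan's own figures.** The only precision figures for the primary outcome are the 95% CIs in Protocol 9.5. Using p ± 1.96·√(p(1−p)/n) with the total AIS counts gives 3.68–4.32%, 4.69–5.31% and 27.29–28.71%, which match the stated 3.7–4.3, 4.7–5.3 and 27.3–28.7. They rest on total AIS counts, not eligible counts, so step 5 assumes a range for the eligible number.

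**Step 2: effect of the exclusion.** After dropping, the proportion is p* = (p − xq)/(1 − x). This equals p only if q = p; it is lower if q > p and higher if q < p.

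**Step 3: size.** With q = 1, x = pm and p* = p(1 − m)/(1 − pm):

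| m | true 4% | true 5% | true 28% |
|---|---|---|---|
| 5% | 3.81% | 4.76% | 26.98% |
| 10% | 3.61% | 4.52% | 25.93% |
| 20% | 3.23% | 4.04% | 23.73% |
| 30% | 2.83% | 3.55% | 21.40% |

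With q = 0 (all dropped patients had non-rtPA IVT or late rtPA, say) and x = 2%, p* = p/0.98 gives 4.08%, 5.10% and 28.57%.

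**Step 4: tipping points (q = 1, one wave affected, none missing in the others).**
- Wave II falls to 4%: 0.05(1 − m)/(1 − 0.05m) = 0.04, so 0.01 = 0.048m and m = 20.8% (x = 1.04% of B).
- Wave I falls to 3%, doubling the gap: 0.01 = 0.0388m, so m = 25.8% (x = 1.03% of B).
- Wave III falls to 5%: 0.23 = 0.266m, so m = 86.5%.

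**Step 5: milder patterns against sampling error.** With m = 20/10/2% by wave, the proportions are 3.23/4.52/27.59% and II − I is 1.30 points. With m = 2/10/20% they are 3.92/4.52/23.73% and II − I is 0.60 points. Against the assumed 1.0 point, the shifts are 0.3 and 0.4. The 95% half-width on II − I is 1.96·√(0.04·0.96/n₁ + 0.05·0.95/n₂). If eligible patients are 5% of the Protocol totals (735 and 980) it is 1.97 points; if 20% (2941 and 3921), 0.98 points. With the SAP's wave I total it is 2.06 and 1.03 points.

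**Step 6: should the main estimate change?** Restoring the dropped patients to B and counting none as in-window gives p − xq. This is further from p than the present estimate whenever q > p/(2 − x), that is, for small x, above about 2%, 2.5% and 14% for p = 4%, 5% and 28%. At m = 20%, q = 1, a true 28% shows as 23.7% under the present rule and 22.4% under the floor. As a pair, the rows do help: at m = 10%, q = 1, the lower row is 3.6/4.5/25.2% and the upper row 4.0/5.0/28.0%.

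**The case against.** A treated patient without a time cannot be classed as inside or outside the 3h or 4.5h window. Dropping such a patient is ordinary complete-case handling, in line with the no-imputation rule (Protocol 9.7.1, SAP 10.2) and the limitation stated in Protocol 9.9. SAP 10.2 also promises to report the amount of missing data and to assess its effect. Protocol 9.6 and SAP 12 describe trained coordinators, independent monitoring and completeness checks for all three forms of data capture. A plan written before analysis cannot be expected to state how many patients will be dropped or which way the result will move. Much of this stands: it supports keeping the present main estimate, and it means that a difference in missingness between waves is possible but not shown. It does not remove the selection on treatment, and SAP 10.2 names no method, bound or count by wave.

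Three stronger readings are tempting.
- That the rule empties B of untreated patients. The literal words allow this, but "Not received IVT" is an exclusion only at the step to C, so untreated patients must still be in B.
- That the proportions are biased downward, or that the rise over time is an artefact. The documents give neither m nor q, and some dropped patients may have had non-rtPA IVT or late rtPA, so even the direction is open.
- That SAP 10.3 leaves all its exclusions without a group. SAP 7.2 and 11.1 assign the missing-data, diagnosis and 7-day exclusions; only the time-contradiction rules have no group.

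Figure 1, the SAP variable definitions, SAP 11.2, Table 2, most dictionary rows and the Protocol subsection after 9.7.1 are not visible. They may contain an 'if treated' limit or a sensitivity analysis. A limit would settle the wording but not the selection.

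**Conclusion.** The point holds, at minor to moderate weight. Item iv lacks a limit to treated patients. On the only workable reading, it and the treatment-time contradiction rules select both primary denominators on treatment, and Tables 1 and 3.1 handle the same patient differently. Size and direction are unknown, and every figure for the shift rests on assumed m and q.

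Within the range tried, the individual wave estimates can move (28% to 25.9% at m = 10%, q = 1), but the assumed rise to 28% is never overturned. The assumed I–II contrast is more fragile. Even so, with q = 1 it is erased only at about 21% missing in wave II with none in wave I, and the milder patterns shift it by less than its sampling error.

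**What to change.** 1. Add 'if IVT was given' to item iv in Protocol 9.2 and SAP 7.2, 10.3 and 11.1, and carry it into the Protocol abstract.
2. Keep the present rule for the main Table 1 estimate; do not replace it with the floor estimate. Report by wave the number of otherwise eligible treated patients dropped for a missing or contradictory IVT time, split by rtPA and other IVT where recorded.
3. Add two supplementary rows to Table 1 that restore these patients to B/B': one counting none of the restored rtPA-treated patients as in-window (lower bound), the other counting all of them (upper bound). Patients given non-rtPA IVT, or added intra-arterial or experimental therapy, enter the denominator only. Read the wave contrasts against these bounds, and name this in SAP 10.2 as the method for the promised assessment.
4. State in SAP 10.3 which group the time-contradiction rules apply to, and that a missing IVT status or time does not remove a patient from group A.

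The cost is wording, one count by wave and a few table rows; no new data are needed. The supplementary numerators will not match N in Tables 3.2.1 and 3.2.2, so a footnote should say why.

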**3) IV-rtPA-treated patients (patient groups C and C')**

1. Inclusion criteria:

- (1) Met the in- and exclusion criteria of "IVT-eligible patients"
- (2) Treated with IV-rtPA within 3h (patient group C) or 4.5h (patient group C') of symptom onset

2. Exclusion criteria:

- (1) Not received IVT
- (2) Received IVT other than rtPA
- (3) Treated with IV-rtPA after 3h (patient group C) or 4.5h (patient group C') of symptom onset
- (4) Received additional treatments with intra-arterial reperfusion or experimental therapies

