### 9.3.2 Outcomes

#### 9.3.2.1 Primary outcomes

For all the three waves of CNSR, the following primary outcomes will be assessed:

- Proportion of patients who received IV-rtPA treatment within 3h of symptom onset (patient group C, please refer to [Figure 1](#) for details on patient groups) among 2h IVT-eligible patients (patient group B);
- Proportion of patients who received IV-rtPA treatment within 4.5h of symptom onset (patient group C') among 3.5h IVT-eligible patients (patient group B').

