## 9.5 STUDY SIZE

It was estimated that in CNSR I, II, and III, the number of total AIS patients is 14704, 19604, and 15204, respectively.

Assuming the IV-rtPA-treated among IVT-eligible patients in CNSR I, II, and III are 4%, 5%, and 28% with the 95% confidence interval (CI) for each wave as below, then which can be distinguished with current study size.

CNSR	I	II	III
Assumed IV-rtPA proportion among eligible patients % (95% CI)	4% (3.7-4.3%)	5% (4.7-5.3%)	28% (27.3-28.7%)

No formal sample size calculation is performed due to the nature of this study. All eligible AIS patients within the existing database from the three waves of CNSR will be included in this study.

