7. RESEARCH METHODS

7.1 STUDY DESIGN

The Chinese treatment guideline for AIS was updated in 2010 where the recommended time window for intravenous recombinant plasminogen activator (IV-rtPA) treatment was extended from 3h since symptoms onset to 4.5h. Along with the development of stroke centers and stroke care quality control system, in order to understand the impact of these efforts on the clinical practices for AIS treatment in China, this study is designed to evaluate the temporal changes from 2007 to 2017, in the IV-rtPA treatment proportion and treatment time intervals of AIS patients.

This study is designed to be non-interventional and exploratory, while the 10-year time window was made possible by combining existing data from three cross-sectional surveys of AIS patients in China: CNSR I (2007-2008), II (2012-2013), and III (2015-2017).

Patients in each of the CNSR waves will be divided into 3 major groups respectively: (1) all AIS patients, (2) IVT-eligible patients (arrival within 2h & 3.5h since symptom onset and without documented absolute contraindication), and (3) IV-rtPA-treated patients (treatment within 3h & 4.5h since symptom onset). This stratification allows calculation and description of IV-rtPA treatment proportion and treatment time intervals across the 10-year window. Taken together the demographic and clinical characteristics data embedded in the CNSR studies, the analysis will help to answer the research question, and hope to provide understanding of the gap between clinical practice and guideline recommendation for acute phase stroke care, and to provide evidence linking minimized in-hospital delays for IV thrombolysis with improved AIS outcomes.

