7.2 SETTING

This study will use AIS patient data from CNSR I to III, stretching across a 10-year time frame from 2007 to 2017. CNSR is a nationwide, prospective stroke registry where patients with acute cerebrovascular diseases were continuously enrolled for 8-12 month every 5-year since 2007.

[REDACTED]

[REDACTED]

CNSR I (2007-2008) was conducted in 131 sites across China, including 113 tertiary and 18 urban hospitals, all the included ischemic stroke (IS) patients were older than 18 and within 14 days of onset. CNSR II (2012-2013) was conducted in 219 hospitals nationwide, and all the included IS patients were older than 18 and within 7 days of onset. CNSR III (2015-2017) was conducted in 201 hospitals, AIS or TIA patients aged 18 years and older within 7 days of symptom onset were included.

STUDY POPULATION

All eligible patients from the CNSR I to III will be included. It was estimated that in CNSR I, II, and III, the number of total AIS patient is 12415, 19604, and 15204, respectively.

The study will analyze data for the following patient groups:

(1) All AIS patients (patient group A): the overall AIS patients aged 18-80 years who arrived at hospital within 7 days of symptom onset;

(2) IVT-eligible patients (patient groups B and B'):

Patient group B and B' are subsets of patient group A: AIS patients who arrived at hospital within 2h (patient group B) and 3.5h (patient group B') of symptom onset and with no documented absolute contraindications to IVT treatment;

(3) IV-rtPA-treated patients (patient groups C and C'):

Patient group C is a subgroup of patient group B, while patient group C' is a subset of patient group B': IVT-eligible patients who arrived at hospital within 2h of symptom onset and received IV-rtPA within 3h of symptom onset (patient group C) and those who arrived at hospital within 3.5h of symptom onset and received IV-rtPA within 4.5h of symptom onset (patient group C').

The flow of data selection for each of the three reporting patient groups is depicted in Figure 1 below.

[figure not shown]

Figure 1. Patient groups selected for the time-trend study

The in- and exclusion criteria for each of the reporting groups are listed below:

All AIS patients (patient group A)

Inclusion criteria:

1. Aged 18-80 years
2. Diagnosed with AIS on admission

Exclusion criteria:

1. Missing baseline data including age and gender

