8.2 OUTCOMES

8.2.1 Primary outcomes

For all the three waves of CNSR, the following primary outcomes will be assessed:

- Proportion of patients who received IV-rtPA treatment within 3h of symptom onset (patient group C) among 2h IVT-eligible patients (patient group B);
- Proportion of patients who received IV-rtPA treatment within 4.5h of symptom onset (patient group C') among 3.5h IVT-eligible patients (patient group B').

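### Patients given in-window IV-rtPA plus intra-arterial or experimental therapy leave the numerator but stay in the denominator, so the treatment proportions are understated if any such patients exist

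*Protocol*

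**What the plan says.** The first primary objective (Protocol 8) reads: "To investigate the temporal changes in the proportion of IV-rtPA treatment from 2007 to 2017 among IVT-eligible patients", and it extends to all AIS patients. SAP 8.2.1 gives the first primary outcome as "Proportion of patients who received IV-rtPA treatment within 3h of symptom onset (patient group C) among 2h IVT-eligible patients (patient group B"). The second primary outcome (C' over B') and the secondary proportions among all AIS patients (C and C' over A) are worded in the same way.

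Protocol 9.2 first describes group C in terms of eligibility and timing only: "IVT-eligible patients who arrived at hospital within 2h of symptom onset and received IV-rtPA within 3h of symptom onset (patient group C"). SAP 7.1 says of the grouping: "This stratification allows calculation and description of IV-rtPA treatment proportion and treatment time intervals across the 10-year window". SAP 7.2 confirms the nesting: "Patient group C is a subgroup of patient group B".

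The detailed criteria for C/C' then add a fourth exclusion: "Received additional treatments with intra-arterial reperfusion or experimental therapies". It stands in the protocol abstract, Protocol 9.2, SAP 7.2 (study population) and SAP 11.1, each time for C/C' only.

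**The concern.** Exclusions (1) to (3) for C/C' only restate that the patient received rtPA within the window. Exclusion (4) is different: it removes people who fully satisfy the outcome wording. That may suit the time-interval outcomes, which are computed within C/C'. In a proportion whose denominator is B, B' or A, it moves treated patients in effect to the untreated side.

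The study is about change from 2007 to 2017. If the use of added therapy differed between waves, the size of the distortion would differ too, and part of the reported trend would reflect exclusion (4) and not the use of IV-rtPA.

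**Working it through.** **1. Where the condition applies (visible text)**

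| Place | Condition on added therapy |
|---|---|
| Protocol 9.2 and abstract, criteria for A | none |
| Protocol 9.2 and abstract, criteria for B/B' | none |
| Protocol Annex 3, contraindication lists | none |
| SAP 7.2, criteria for A and B/B' | none |
| SAP 10.3, data exclusions | none |
| Protocol 9.2 and abstract, SAP 7.2 and 11.1, criteria for C/C' | excluded |

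A patient in B who received IV-rtPA within 3h and also had added therapy counts in N and not in n. The same holds for B' and for A.

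**2. Formula**

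Let N be the size of the denominator, T the number in it who arrived and received IV-rtPA within the stated windows and meet the other C/C' criteria, and b the share of T with added therapy. The proportion as worded is p = T/N. The reported proportion is T(1 − b)/N = p(1 − b), which is below p for any b > 0.

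Example: of 1,000 eligible patients, 280 receive in-window IV-rtPA and 28 of these also have added therapy (b = 10%). The plan reports 252/1,000 = 25.2%, not 28.0%. Removing the 28 from the denominator as well would give 252/972 = 25.9%, so that does not restore the proportion as worded either.

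**3. The plan's own figures**

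Protocol 9.5 assumes 4%, 5% and 28% for waves I, II and III, with 95% intervals 3.7–4.3%, 4.7–5.3% and 27.3–28.7%. The formula p ± 1.96·√(p(1 − p)/n), with n the total AIS patients (14704, 19604, 15204), gives 3.68–4.32, 4.69–5.31 and 27.29–28.71. These agree. The stated intervals thus use all AIS patients as n, although the proportion is among eligible patients.

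**4. Size, with b assumed**

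The protocol does not say whether 4/5/28% stand before or after exclusion (4), so both readings are shown.

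*Reading 1: the figures are p, before the exclusion. Reported = p(1 − b).*

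| b in waves I / III | Wave I | Wave III | Change I to III (points) | Ratio III/I |
|---|---|---|---|---|
| 0 / 0 | 4.00% | 28.00% | 24.0 | 7.0 |
| 5% / 5% | 3.80% | 26.60% | 22.8 | 7.0 |
| 10% / 10% | 3.60% | 25.20% | 21.6 | 7.0 |
| 0 / 10% | 4.00% | 25.20% | 21.2 | 6.3 |
| 7% / 1% | 3.72% | 27.72% | 24.0 | 7.45 |

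At b = 2%, wave III would be reported as 28 × 0.98 = 27.4%. A constant b shrinks the absolute change and leaves the ratio alone. A b that differs between waves moves the ratio and generally the change as well. The change is untouched only when 4·b(I) = 28·b(III); the last row is such a case.

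*Reading 2: the figures are the reported values, after the exclusion. As worded, p = reported/(1 − b).* For wave III: 28/0.98 = 28.6%, 28/0.95 = 29.5%, 28/0.90 = 31.1%. With b = 0 in wave I and 10% in wave III, the change as worded is 31.1 − 4.0 = 27.1 points, against a reported 24.0.

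**5. Against sampling error**

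The wave III shift is 28·b points. It passes the protocol's stated half-width of 0.7 points once b > 0.7/28 = 2.5%. That half-width rests on all AIS patients, so this yardstick is too strict. If eligible patients were 10–20% of 15204 (an assumption), the half-width at 28% would be about 2.3–1.6 points, and b would have to exceed about 8–6%.

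**The case against.** The strongest reply is that the calculation is not ambiguous. Every proportion outcome names C or C' as its numerator, the exclusion is stated consistently wherever the criteria for C/C' are listed, and the short group descriptions are followed by full criteria. The mock-table label for 3h IV-rtPA can be read as shorthand for group C. If the sponsor wants IV-rtPA without added therapy, C/B is exact and only the label is too short. In addition, b is not given and could be zero, and the rise to wave III survives every value tried. Figure 1 and parts of the outcome and analysis sections are not visible, so separate handling there is possible.

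Much of this stands. The number to compute is determined, its distance from the outcome as worded is unknown, and hidden text could already deal with the point. It does not settle the matter, because the objective, the outcome lines and the short definitions all describe receipt of IV-rtPA, and no visible text says that these recipients are to be left out of the proportion or why. A reader of Table 1 would take n/N as the share who received the drug in time. Relabelling would be a legitimate answer, but it too is a change to the plan.

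**Conclusion.** The concern holds on the visible text, and the plan should be changed. The direction is certain: the reported proportion is below the proportion as worded by the relative amount b, for both primary outcomes and both secondary proportions. The size is unknown, because the documents give b for no wave. On the plan's own 4% and 28%, assumed values of b up to 10% move wave III by up to 2.8 points under reading 1 and 3.1 points under reading 2. The change between waves I and III moves by about 3 points when b is 0 in wave I and 10% in wave III. Near b = 0 the effect is negligible. This is a primary estimate that does not match its label, with a possible distortion of the trend; it does not reverse the expected conclusion. Confidence is medium, because Figure 1 and some analysis text cannot be seen.

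**What to change.** Define a separate numerator in Protocol 9.2 and in SAP 7.2 and 11.1, for example: *T/T' = all members of B/B' who received IV-rtPA within 3h/4.5h of onset, whether or not they had additional intra-arterial or experimental therapy.* Use T/T' in place of C/C' in each proportion outcome (Protocol abstract, 9.3.2.1 and 9.3.2.2; SAP 8.2.1, 8.2.2, 11.1.1 and 11.1.2) and in mock Tables 1 and 3.1. Keep C/C' with exclusion (4) for the time-interval and characteristics tables.

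In Tables 1 and 3.1, report per wave how many T/T' patients exclusion (4) removes, and show the C/C'-based proportion as a labelled additional row. Add a footnote on why n in Table 1 differs from N in Tables 3.2.1 and 3.2.2.

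If the sponsor instead intends IV-rtPA without added therapy, say so in the outcome lines and row labels, and still report the removed count per wave. A count of zero would close the point.

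The cost is one definition, wording edits in seven outcome sections, an extra row for each of the 3h and 4.5h lines in two tables, the counts and a footnote. The alternative needs only the label edits and the counts. No new data should be needed, since exclusion (4) already requires these patients to be identified. The readable rows of the SAP variable dictionary do not name that variable and most rows are redacted, so its availability in each wave should be confirmed.
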